### 11.2.2 Assessment of Adverse Event Severity and Relationship to Treatment

The following scale will be used to “grade” the severity of all adverse events.

- 1 Mild. Awareness of sign, symptom, or event, but easily tolerated; does not interfere with usual daily activities or tasks.
- 2 Moderate. Discomfort enough to cause interference with usual daily activity; may warrant therapeutic intervention.
- 3 Severe. Incapacitating; inability to perform usual activities and daily tasks; significantly affects clinical status; requires therapeutic intervention.
- 4 Life-threatening. Adverse event is life-threatening.
- 5 Death. Adverse event causes death.

The standard nomenclature for defining the causal relationship between an AE and the study drug used by CSCC is listed in the following table. The category that overall best “fits” the relationship between the adverse event and the study drug should be chosen.

Unrelated	
 
• No temporal association to study product.
 
• An alternate etiology has been established.
 
• The event does not follow the known pattern of response to study product.
 
• The event does not reappear or worsen with re-challenge.
 

Probably not related / remote	
 
• No temporal association to study product.
 
• Event could readily be produced by clinical state, environmental or other interventions.
 
• The event does not follow the known pattern of response to study product.
 
• The event does not reappear or worsen with re-challenge.
 

Possibly related	
 
• Reasonable temporal relationship to study product.
 
• The event is not readily produced by clinical state, environmental, or other interventions.
 
• The event follows a known pattern of response to the study product or as yet unknown pattern of response.
 

Probably related	
 
• There is a reasonable temporal association with the study
 

	
product.
 
 
• The event is not readily produced by clinical state, environmental, or other interventions.
 
• The event follows a known pattern of response to the study product.
 
• The event decreases with de-challenge.
 

Definitely related	
 
• There is a reasonable temporal relationship to the study product.
 
• The event is not readily produced by clinical state, environmental, or other interventions.
 
• The event follows a known pattern of response to the study product.
 
• The event decreases with de-challenge and recurs with re-challenge.
 

### 11.2.3 Outcome of Adverse Events

Every AE must be followed to a satisfactory outcome or stabilization of the event, even when this requires a time period beyond the scope of the study (this is particularly applicable to serious adverse events (SAEs)). Outcome is defined as

**Outcome: Information on recovery and any sequelae; what specific tests and/or treatment may have been required and their results. For a fatal outcome, cause of death and a comment on its possible relationship to the suspected reaction should be provided.**

The terms used to define outcome are as follows (outcome of reaction/event at the time of last observation):

- Ongoing
- Resolved without sequelae
- Resolved with sequelae
- Death

Actions taken in response to an AE and follow-up results must be recorded in the subject's medical record (this includes follow-up laboratory results). Any treatment administered for the adverse event must be recorded in the subject's CRF. When subjects are discontinued from the study due to an AE, relevant clinical assessments and laboratory tests will be repeated as necessary until final resolution or stabilization occurs.

#### *11.2.4 Reporting of Adverse Events*

Serious safety issues that arise in this study will be brought to the attention of the CSCC Data and Safety Monitoring Board (the “DSMB”), which will make recommendations to the NHLBI regarding possible suspension of the study. The NHLBI will consider the DSMB’s recommendations, determine an appropriate action and notify the Principal Investigator and the CSCC Statistics and Data Management Center (SDMC). The Principal Investigator will notify all participating investigators, who will implement the actions directed by NHLBI. This section defines “serious safety issues” and describes procedures for bringing them to the attention of the DSMB.

This study is being conducted under an Investigational New Drug Application (“IND”). Consequently, U.S. Government regulations require that all “unexpected serious adverse events” (defined below) must be reported to the Food and Drug Administration (FDA) within either 7 calendar days (fatal or life-threatening events) or 15 calendar days (non-fatal, non-life-threatening). These Suspension Guidelines require that unexpected serious adverse events also be reported to the DSMB within the same timeframe. The FDA has the authority to direct the investigators to suspend or terminate the study, or take other actions.

These Guidelines specify the following types of reports that can alert the DSMB to a potential safety issue:

- Ad hoc reports of unexpected serious adverse events that are made within 7 or 14 calendar days, as specified in subsequent paragraphs.
- Reports of quarterly statistical analyses of all serious adverse events. The SDMC makes such analyses quarterly, but files a report to the DSMB only when analyses indicate that a safety issue has arisen, as defined by the “alert” criteria.

Semi-annual DSMB reports of analyses of adverse events and of clinical laboratory results. These reports will highlight any safety issues revealed by the analyses that meet the “alert” criteria.

#### *11.2.5 Reporting of Unexpected Serious Adverse Events*

Within 8 hours of the realization that an unexpected SAE has occurred to a study subject, a study investigator must make an initial report:

- To the Principal Investigator.
- To the CSCC Statistics and Data Management Center SAE Regulatory Specialist.

The investigator must also report the unexpected SAE to the site’s IRB in accordance with that IRB’s regulations or procedures.

The site investigator, the Principal Investigator, and the SDMC SAE Regulatory Specialist will collaborate to prepare a report of the unexpected SAE using the current version of FDA's SAE reporting forms. The report should describe the event as fully as possible. The initial SAE reports received from the site should include the following minimum information: an identifiable subject; study product; an identifiable reporting source; and an event or outcome that can be identified as serious. Supporting documentation (CRF pages, lab reports, summary notes, autopsy reports) should accompany the report.

A fatal or life-threatening unexpected SAE will be reported to the DSMB [and FDA] within 7 calendar days of the receipt of the initial report by the SDMC SAE Regulatory Specialist. A non-fatal, non-life-threatening unexpected SAE will be reported to the DSMB [and FDA] within 15 calendar days of the receipt of the initial report by the SDMC SAE Regulatory Specialist.

The Principal Investigator will submit the DSMB report to the Chair of the DSMB Subcommittee appointed to monitor this study and to the NHLBI Project Officer. The Principal Investigator will submit the unexpected SAE report to all study investigators. Each study investigator will submit the unexpected SAE report to the local IRB and other local authorities in accordance with the institution's regulations.

All serious adverse events, regardless of expected status, are also recorded in the Adverse Events section of the study's case report form.

The site investigator will follow the progress of a subject who experiences an unexpected SAE until the SAE is resolved. When the unexpected SAE has not resolved by the report deadline, the site investigator will make followup reports in accordance with directions from the DSMB, the FDA, and/or the site's IRB.

#### *11.2.6 Reporting of Expected Serious Adverse Events*

Within 3 days of the realization that an expected SAE has occurred to a study subject, a study investigator must make an initial report:

- To the Principal Investigator
- To the CSCC Statistics and Data Management Center SAE Regulatory Specialist

The investigator must also report the expected SAE to the site's IRB in accordance with the IRB's regulations or procedures.

Three months after the first subject is enrolled in the study, and at the end of each 3 months thereafter, if any SAEs (expected or unexpected) have been reported in the study during the preceding 3 months, the SDMC will:

- Use the current version of the MedDRA dictionary to code all AEs (serious or not) that have been recorded on study AE forms.
- Make a “snapshot” copy of the adverse events data, including MedDRA codes.
- Create frequency tables of treatment x occurrence (yes or no, since inception of the study) of all patients. One table will be created for each highest level MedDRA term for which SAEs have been reported. The counting units are patients, not events.
- Compute Fisher’s Exact Test (FET) statistic to test the alternative hypothesis that occurrence of SAEs is not independent of treatment group. The FET p-value is not adjusted for multiplicity.
- If the FET p-value is less than the critical value shown in Table 3 and the active treatment group has a higher AE rate, the SDMC will conduct further statistical analyses as indicated by the circumstances and report the results to the Chair of the DSMB subcommittee monitoring this study, the Principal Investigator, and the NHLBI Project Officer.
- The SDMC will not file a report of expected SAEs if none of the FET p-values is less than the critical value shown in Table 3 or if the relative risk is less than 1.

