## 5 BACKGROUND AND RATIONALE

### 5.1 Sickle Cell Disease

Sickle cell disease (SCD) is a genetic disease which results from a point mutation at codon 6 which substitutes a valine for glutamine in the  $\beta$  globin protein of hemoglobin. The resulting sickle hemoglobin polymerizes abnormally when deoxygenated forming a rigid fiber. This fiber of polymerized hemoglobin distorts the shape of the cell and causes the characteristic sickle-shaped red cell that gives this disease its name. The clinical manifestations of SCD result from the resulting hemolytic anemia and vaso-occlusion (VO). The anemia of SCD is fairly well tolerated but VO results in most of the morbidity of SCD. As a result of VO, patients with (SCD) suffer from many different clinical manifestations affecting nearly every organ system in the body. The more common vaso-occlusive manifestations that affect these patients include pain episodes, severe pneumonia, overwhelming infections, stroke, and aseptic necrosis of the hip.

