## 6 STUDY OBJECTIVES AND PURPOSE

The primary and secondary objectives of the study are as follows:

Primary Objectives:

- **To assess the physiological effects (both beneficial and deleterious) of the administration of oral arginine in patients with SCD.**

We will initiate a double blinded, placebo controlled phase II trial where SCD patients will receive placebo or a dose of arginine hydrochloride orally for 12 weeks. We will comprehensively assess the physiological effects of arginine administration throughout this clinical trial. These investigations will focus on three target areas— sickle erythrocyte characterization, free radical biology/damage, and endothelial function.

Secondary Objectives:

- **To evaluate the effect of daily oral arginine on clinical vaso-occlusive events in SCD patients.**

Clinical efficacy will be a secondary endpoint of the clinical trial, but patients will be assessed regularly to determine if arginine treatment results in a reduction in clinical VO events or patient reports of pain.

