#### *11.2.7 Reporting of All Other Adverse Events*

For any and all adverse events, study coordinators and/or Principal Investigators will use the standard procedure of documenting the event using the Adverse Events Case Report Form.

Six months after the first subject is enrolled in the study, and at the end of each 6 months thereafter, the SDMC will:

- Use the current version of the MedDRA dictionary to code all AEs that have been recorded on study AE forms.
- Make a “snapshot” copy of the adverse events data, including MedDRA codes.
- Create frequency tables of treatment x occurrence (yes or no, since inception of the study) of all patients. One table will be created for each highest level MedDRA term for which AEs have been reported. The counting units are patients, not events.
- Compute Fisher’s Exact Test (FET) statistic to test the alternative hypothesis that occurrence of AEs is not independent of treatment group. The FET p-value is not adjusted for multiplicity.
- If the FET p-value is less than the critical value shown in Table 3 and the active treatment group has a higher AE rate, the SDMC will conduct further statistical analyses as indicated by the circumstances and alert the DSMB to this finding in the semi-annual DSMB report.
- Collaborate with the Principal Investigator to incorporate the results into the study’s semi-annual report to the DSMB and the NHLBI Project Officer.

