### 11.2.8 Reporting of Safety Laboratory Measures

Six months after the first subject is enrolled in the study, and at the end of each 6 months thereafter, the SDMC will:

- Make a “snapshot” copy of the study’s clinical laboratory data.
- Perform an appropriate statistical analysis of clinical laboratory change-from-baseline data for each clinical laboratory evaluation obtained in this study.
- Perform an appropriate statistical test of:  $H_0$ : The mean (or median, or proportion, as appropriate) change-from-baseline of the clinical laboratory values for the active treatment group is the same as for the placebo group, vs.  $H_a$ : The mean (or median, or proportion) change-from-baseline in the active treatment group is “worse” than for the placebo group. The meaning of “worse” depends upon the specific clinical lab measurement. The test statistic p-value is not adjusted for multiplicity.
- If the hypothesis test p-value is less than the critical value shown in Table 3, the SDMC will conduct further statistical analyses as indicated by the circumstances and highlight this finding in the semi-annual DSMB report.
- Collaborate with the Principal Investigator to incorporate the results into the study’s semi-annual report to the DSMB and the NHLBI Project Officer.

Table 11.3. Summary of Procedures and Timing for Alerting the DSMB and NHLBI Project Officer of Possible Serious Safety Issues

Situation or Event	Summary of Procedure (See text for details.)	Critical Value for DSMB “Alert”
Unexpected SAE	1. Site investigator notifies SDMC SAE Regulatory Specialist and Principal Investigator within 8 hours.	Alert all cases.
	2. Site investigator, SDMC SAE Regulatory Specialist and Principal Investigator prepare report using FDA forms and submit report to DSMB, NHLBI Project Officer, IRBs, study investigators. Report: 1. Fatal or life-threatening: within 7 calendar days. 2. Otherwise: within 14 calendar days.	Alert all cases.
Expected SAE	SDMC performs quarterly analyses of MedDRA-coded SAEs, tabulates patients with SAEs classified by highest level MedDRA term. Report only when $p <$ critical value and active treatment group has higher AE rate.	$p < 0.01$ $p$ not adjusted for multiplicity

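### The safety alerts are tested only within each highest-level MedDRA term, with no any-SAE or any-AE table, which can sharply reduce the chance that a general worsening triggers a quarterly alert

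*Protocol*

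**What the plan says.** Section 11.2.6 has the data center run, every three months, a Fisher exact test of occurrence by treatment, cumulative from the start of the study. The unit of the table is fixed: "One table will be created for each highest level MedDRA term for which SAEs have been reported". Patients are counted once per table ("The counting units are patients, not events"). The test is two-sided in form, since it is to "test the alternative hypothesis that occurrence of SAEs is not independent of treatment group", with the added condition that the active group has the higher rate. The limit in Table 11.3 is p < 0.01 without adjustment. If no term reaches it, no report of expected SAEs is filed.

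Table 11.3, in section 11.2.8, repeats the unit: the quarterly analysis "tabulates patients with SAEs classified by highest level MedDRA term". The semi-annual analysis of all AEs in section 11.2.7 is built the same way: "One table will be created for each highest level MedDRA term for which AEs have been reported".

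Section 11.2.4 announces quarterly analyses of all SAEs. That might suggest an overall comparison, but section 11.2.6 carries it out term by term and speaks of several p-values.

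**The concern.** Section 5.1 says that, through vaso-occlusion, patients "suffer from many different clinical manifestations affecting nearly every organ system in the body". Table 11.1 accordingly lists complications of lung, brain, kidney, bone, spleen and eye, together with priapism and several kinds of pain, as expected events. Expected SAEs do not go to the DSMB case by case, so the term-level tests are their only statistical trigger for a quarterly report.

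Section 6 includes deleterious effects in the primary objective, and the secondary objective is "To evaluate the effect of daily oral arginine on clinical vaso-occlusive events in SCD patients". If arginine made the disease worse in general, the excess could fall across several terms. Each table would then hold a modest imbalance, and none would count the patients affected overall.

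**Working it through.** **The plan's own figure.** The protocol states no detection probability for the alert, so there is none to reproduce.

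**Inputs from the protocol.**
- Rule: two-sided Fisher exact p < 0.01 and a higher rate on arginine (11.2.6, Table 11.3).
- Arms (section 7.2): 16 placebo and 16 low dose per age group, so 16 + 16 = 32 per arm over both ages. The closed high-dose arm has 16 + 14 = 30, so 32 v 62 if both doses are pooled. Section 11.2.6 does not say whether doses or ages are pooled, so more than one configuration is shown.

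**Assumptions.** SAE rates, the number of terms and the way patients spread over them are not in the protocol.

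**What a single table needs.** At 32 v 32, 0 v 7 gives p = 0.0108 and 0 v 8 gives p = 0.0048; with 2 placebo cases, 12 arginine cases are needed. At 16 v 16, 0 v 6 gives p = 0.018 and 0 v 7 gives p = 0.0068.

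**One concrete split.** At 32 v 32, 8 v 20 patients with any SAE gives p = 0.005 and would alert. Divided evenly over four terms, each table holds 8/4 = 2 v 20/4 = 5. Each gives p = 0.43, and nothing alerts.

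**Chance of an alert.** Let p be the any-SAE risk and K the number of even terms.
- Independent terms: risk per term q = 1 − (1 − p)^(1/K). If one table alerts with probability a, the chance of at least one alert is 1 − (1 − a)^K.
- Each affected patient in one term only: q = p/K.
- Concentrated: the leading term has risk c × p, with c = 0.7 to 0.9, and only that table is counted.

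For K = 4 and 20% v 60%, independent terms have q = 1 − 0.8^(1/4) = 5.4% v 1 − 0.4^(1/4) = 20.5%. With one term per patient, q = 5% v 15%.

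| Arms | Any SAE | One any-SAE table | K = 3 to 6, independent | K = 3 to 6, one term each |
|---|---|---|---|---|
| 32 v 32 | 20% v 60% | 70.5% | 44% to 15% | 18% to 2.5% |
| 32 v 32 | 20% v 50% | 39.6% | 17.7% to 3.8% | 7.6% to 0.8% |
| 32 v 62 | 20% v 60% | 88% | 70% to 30% | 38% to 4% |

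At 16 v 16 and 20% v 60%, the any-SAE table alerts in 28%, against 5% for four independent terms.

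**Concentration.** At 32 v 32 and 20% v 60%, a single term holding 70%, 80% or 90% of affected patients alerts in 37%, 49% or 60%.

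**Event rate.** Taking one event per patient-year over 16 weeks gives 16/52 = 0.31 events per patient. If that rate is tripled at 32 v 32, the chance of an alert is 46% in one table, 35% if 70% of events fall in one term, 21% over four even terms and 11% over six. At 0.5 events per patient tripled, the figures are 64%, 53%, 49% and 36%. At 1.0 per patient tripled, one table alerts in 65% and four even terms in 87%, so splitting loses nothing there.

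**A smaller harm.** For a doubling (20% v 40%) at 32 v 32, the any-SAE table alerts in about 14% and four independent terms in 2.5%.

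**No effect.** At 20% v 20%, the added table alerts falsely in 0.17% of looks at 32 v 32 and 0.31% at 32 v 62.

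**The case against.** The best defense is that class-level screening with DSMB review behind it is a coherent design and contradicts nothing in the protocol. Four parts of that case have weight.

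- **The even split is an assumption.** The protocol does not map Table 11.1 to MedDRA terms. Entry requires a pain event, and the only event forecast, in section 12.1, concerns pain episodes, so SAEs may well concentrate in one term. This stands, and it narrows the loss. Even so, a term holding 70% of affected patients alerts only about half as often as the pooled table (37% against 70.5%).
- **Small arms and p < 0.01 limit detection as well.** This stands. The any-SAE table would still miss most doublings, and early quarterly looks have fewer patients than the final figures used here.
- **Other routes reach the DSMB.** This stands. The AE analysis enters the semi-annual report whether or not an alert fires, unexpected SAEs are reported case by case, and section 13.1 has the DSMB examine unblinded safety data periodically. However, the semi-annual alert uses the same class-only rule, and section 13.1 names no schedule or comparison.
- **A vaso-occlusive composite would overlap a secondary efficacy endpoint**, while section 12.4.5 rules out interim analyses. This stands against making such a table a requirement, but not against an any-SAE table.

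A reader might infer that the class tables are too sparse ever to alert, or that a general worsening would go unseen. The documents do not support either reading. Concentrated or frequent events can alert in a class table, and the rule against filing covers only the quarterly report of expected SAEs.

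**Conclusion.** The point holds as a weakness in the early trigger. The SAE and AE alerts are defined by highest-level term only, no section supplies an overall table, and a diffuse excess can therefore lose much of its chance of a quarterly alert. With 20% v 60% at 32 v 32, that chance falls from about 70% to between 2.5% and 44% over three to six even terms, and to 37% to 60% if one term dominates. With both doses pooled, it falls from 88% to between 4% and 70%. These figures rest on assumed SAE rates, an assumed spread over terms, the final sample size and a single look. They show how large the loss can be and do not forecast it: near one event per patient it disappears. The change is worth making because it is cheap and repairs a rule the protocol already fixes. It would not make the alert sensitive to moderate harm.

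**What to change.** In section 11.2.6 and the Expected SAE row of Table 11.3, add one table per quarterly run counting patients with any SAE, under the same Fisher p < 0.01 and direction rule. In section 11.2.7 and the matching row of Table 11.3, add a table of patients with any AE. Keep the class tables. State whether the tests pool ages and doses, and give the detection probability under declared rates.

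The cost is one more table per quarter and one per half-year, from data already coded. The any-SAE table adds one unadjusted test per look, with about 0.2% false alerts at 32 v 32 and 0.3% at 32 v 62 when both groups have 20%; repeated looks add to this.

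A vaso-occlusive SAE table is optional. If it is added, fix its term list in advance and state that it is DSMB safety monitoring, separate from the rule in section 12.4.5 against interim analyses.

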Bone infarction	Elevated urinary urobilinogen	Skin ulcers
Cardiomegaly	Fever	Splenic sequestration
Cerebrovascular accident	Hand-foot syndrome	Pain, joint
Cholecystitis, hepatic sequestration	Hematuria	Pain, long bone
Cranial nerve palsy	Hemiplegia	Pain, severe abdominal
Decreased kidney function	Hemolysis	Priapism
Decreased lung function	Hepatosplenomegaly	Pulmonary embolism
Delayed growth/puberty	Hyperplastic bone marrow	Pulmonary hypertension
Depressed ESR	Hyposthenuria	Pulmonary parenchymal infiltrates on chest x-ray

Table 11.2. Overview of Definitions of Safety Measures

Word or Phrase and (Abbreviation)	Definition
Adverse event (AE)	Any untoward clinical or medical occurrence.
Serious adverse event (SAE)	Any adverse event that results in any of the following outcomes: Death, a life-threatening adverse event, inpatient hospitalization or prolongation of existing hospitalization, a persistent or significant disability/incapacity, or a congenital anomaly/birth defect.
Expected Serious Adverse Event (Expected SAE)	An expected SAE for subjects in this study is an adverse event that is listed in Table 11.1 and is a serious adverse event, as defined above.
Unexpected Serious Adverse Event (Unexpected SAE)	An unexpected SAE for subjects in this study is any AE that is not listed in Table 11.1 and is a serious adverse event, as defined above.
Adverse Clinical	Any safety laboratory measurement that is measured beyond the

Laboratory Results	acceptable limits (either high or low) for the population being studied, as described by the investigator.
--------------------	--

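### Fatal and life-threatening events on the expected list have no prompt route to the DSMB, and the quarterly Fisher test does not supply one

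*Protocol*

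**What the plan says.** **Who counts as expected.** Protocol section 11.2.1 and Table 11.2 define an expected SAE as "an adverse event that is listed in Table 11.1 and is a serious adverse event, as defined above". Table 11.1 is a list of terms. Among them are acute chest syndrome, cerebrovascular accident, sepsis, meningitis, pulmonary embolism, splenic sequestration and renal failure. Neither severity nor outcome enters the definition, although section 11.2.2 has separate grades for life-threatening events (4) and death (5).

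**Expedited route.** Section 11.2.5: "A fatal or life-threatening unexpected SAE will be reported to the DSMB" within 7 calendar days of the SDMC receiving the first report. Sections 11.2.4 and 11.2.5 and Table 11.3 all confine the expedited DSMB report to unexpected SAEs.

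**Route for listed events.** Section 11.2.6 sends an expected SAE to the Principal Investigator and the SDMC within 3 days, and to the site IRB. It has no DSMB step for the individual event. Each quarter the SDMC runs Fisher's exact test to "test the alternative hypothesis that occurrence of SAEs is not independent of treatment group", and "One table will be created for each highest level MedDRA term for which SAEs have been reported". Section 11.2.4 says that the SDMC "files a report to the DSMB only when analyses indicate that a safety issue has arisen". Section 11.2.6 puts it as a prohibition: "The SDMC will not file a report of expected SAEs if none of the FET p-values is less than the critical value". Table 11.3 sets that value at 0.01, unadjusted, and also requires that the active group have the higher rate. (Section 11.2.6 cites a Table 3; the values stand in Table 11.3.)

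**Routes that do not depend on a p-value.** Section 11.2.7 and Table 11.3 put AE results into a DSMB report every six months, with only the alert flag depending on p<0.01. Section 13.1 has the DSMB look periodically at unblinded safety data, at an interval that is not stated.

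**The concern.** The listed terms include the complications most likely to kill a patient with sickle cell disease. A death from one of them on study drug is handled as an expected SAE, so the board that advises on suspending the trial is not told promptly. Whether it hears at the next quarter depends on a significance test.

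That test suits the purpose poorly. It needs many events in a trial of this size. Deaths have no table of their own: they are mixed with non-fatal SAEs under the same MedDRA term, and deaths from different causes may fall in different tables. One or two deaths are the kind of information a board would want case by case, and no test at 0.01 can bring them forward here.

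**Working it through.** **1. Table sizes (section 7.2).** Each age group has 16 low-dose and 16 placebo patients. The closed high-dose arm adds 16 children and 14 adults.

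- Low dose: 16 + 16 = 32. Placebo: 16 + 16 = 32. High dose: 16 + 14 = 30.
- Total: 32 + 32 + 30 = 94, which reproduces the protocol's figure. Pooled active: 32 + 30 = 62.

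The protocol does not say whether the quarterly table has two groups or three. Its reference to the active treatment group in the singular suggests two. Both readings are shown.

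**2. Smallest count that passes, with no placebo events.** The stated alternative is non-independence, so the test is two-sided. For equal arms of size n with all k events on one side, p = 2·C(n,k)/C(2n,k). At n = 32:

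- k = 7: p = 0.0108, which fails.
- k = 8: p = 2 × 10,518,300 / 4,426,165,368 = 0.0048, which passes.

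For unequal arms, p is the sum of the hypergeometric probabilities of all tables no more likely than the one observed.

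| Table at full enrolment | Last failing count | First passing count |
|---|---|---|
| Low dose v placebo, 32 v 32 | 7 v 0, p=0.0108 | 8 v 0, p=0.0048 |
| Pooled active v placebo, 62 v 32 | 11 v 0, p=0.0140 | 12 v 0, p=0.0070 |
| One age group, low dose v placebo, 16 v 16 | 6 v 0, p=0.0177 | 7 v 0, p=0.0068 |
| High dose v placebo, 30 v 32 | 5 v 0, p=0.0220 | 6 v 0, p=0.0097 |
| Three arms, all events in high dose | 3, p=0.0303 | 4, p=0.0090 |
| Three arms, all events in low dose | 4, p=0.0326 | 5, p=0.0099 |

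Three-arm check (Fisher-Freeman-Halton, arms 30/32/32): four events all in the high-dose arm form the least likely table, so p = C(30,4)/C(94,4) = 27,405/3,049,501 = 0.0090. If events are spread evenly over the two arginine arms, 12 events still fail (p=0.0160) and 13 pass (p=0.0081). A single placebo event raises the requirement to 10 v 1 at 32 v 32 and to 15 v 1 at 62 v 32.

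**3. Excess of 1 to 3, no placebo events.** The smallest p among these is 0.0303 (three arms, 3 in high dose). In the two-group tables, 3 v 0 gives 0.24 (32 v 32), 0.55 (62 v 32), 0.23 (16 v 16) and 0.11 (30 v 32). None passes.

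**4. Chance of passing.** The protocol gives no SAE or death rates, so the rates below are assumptions. They refer to patients with any SAE under one MedDRA term. The probability is the sum, over all pairs of binomial counts, of those with p<0.01 and the higher rate on active.

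| Assumed rate, placebo v active | 32 v 32 | 62 v 32 |
|---|---|---|
| 0% v 10% | 1.2% | 1.9% |
| 10% v 30% | 18% | 31% |
| 10% v 40% | 49% | 70% |

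For 0% v 10% in both arginine arms, the three-arm table gives 7.9%.

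**5. Time to the DSMB.** An event just after a semi-annual data snapshot waits about six months (about 26 weeks) for the next. Treatment lasts 12 weeks and the last visit is at week 16, so a patient randomized just after one snapshot can finish before the next. Enrolment is planned over 18 months (section 12.1), so other patients would be entering and taking study drug during the wait. On the expedited clock the longest path would be 3 days to the SDMC plus 7 days, or 10 days.

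**The case against.** Limiting expedited reports to unexpected SAEs, and summarizing common disease complications periodically, is a deliberate and internally consistent scheme. It keeps routine pain admissions from flooding the board. That reasoning stands for non-fatal listed events. It does not extend to deaths and life-threatening events, which would add few reports.

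A reader might infer that a clear excess of deaths on arginine would never reach the DSMB. The documents do not support that. The semi-annual AE results go to the board whatever the p-value (section 11.2.7, Table 11.3), and section 13.1 provides for periodic review of unblinded safety data with power to recommend stopping at any time. Nor are these events hidden from everyone: the Principal Investigator, the SDMC and the IRB are told, and the individual discontinuation criteria in sections 8.3, 9.1.2 and 11.2.9 operate without the DSMB. What is missing is prompt review by the DSMB itself.

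A reader might also take the alert probabilities as the chance of detecting excess deaths. They are not: the tested count is patients with any SAE per term, the rates are assumed, and the answer changes with the table layout. The two-group layout is likely but not settled, and a three-arm table can pass with as few as 4 events if all fall in one arginine arm.

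**Conclusion.** The gap is real and narrow. A fatal or life-threatening event on the Table 11.1 list has no expedited path to the DSMB, and the quarterly filing does not replace it. With no placebo events at full enrolment, the filing requires 6 to 12 patients in the two-group tables and at least 4, all in one arginine arm, in a three-arm table. An excess of 1 to 3 passes in none of them. These counts rest only on the protocol's arm sizes and its 0.01 threshold; the alert probabilities rest on assumed rates as well.

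The consequence is a delay of up to about six months, shorter if a periodic DSMB review falls sooner. The semi-annual report would then normally carry the events unflagged, because it uses the same threshold. This should be fixed, but it is not a failure that leaves the DSMB permanently unaware.

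**What to change.** In sections 11.2.4 to 11.2.6 and Table 11.3, state that every fatal or life-threatening SAE is reported to the DSMB on the existing 7-day clock, whether or not its term is in Table 11.1. Keep p<0.01 for flagging the remaining expected SAEs. The change concerns DSMB notification only; FDA reporting of unexpected SAEs can stay as written. While editing, state whether the quarterly table has two groups or three, and correct the reference to Table 3.

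Optionally, send the quarterly SAE table by arm to the DSMB in each quarter in which it is produced. The SDMC already prepares it, so this is a preference and not a condition of the fix.

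The cost is a protocol edit and a few more DSMB transmissions. Sample size, randomization and the efficacy analysis are unaffected.
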